## SCHEMA

Phase I: 12 patients who undergo SBRT and surgical resection

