### **2.3 Secondary Objectives**

- a) To determine local control and recurrence patterns of treated patients relative to historical controls.
- b) To determine progression free survival of treated patients
- c) To determine overall survival of treated patients

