### **3.2 Inclusion Criteria**

- a) Patient with pathologically proven diagnosis of adenocarcinoma of the head of the pancreas
- b) CT w/ contrast or MRI of the abdomen with contrast within 6 weeks prior to registration
- c) CT chest or PET/CT within 6 weeks prior to registration
- d) Clinically determined to be resectable based on NCCN Criteria:

- e) No radiographic evidence of superior mesenteric vein or portal vein distortion
- f) No evidence of distant metastasis
- g) Clear fat planes around the celiac axis, hepatic artery, and superior mesenteric artery
- h) No enlarged lymph nodes per CT criteria or PET avid lymph nodes
- i) No lymphadenopathy outside the surgical field (i.e. celiac or para-aortic adenopathy)
- j) Adequate cardiopulmonary reserves to tolerate surgery
- k) Karnofsky performance status  $\geq 70$
- l) Age  $\geq 18$
- m) Adequate bone marrow function defined as follows:
  - Absolute neutrophil count (ANC)  $\geq 1800$  cells/mm^3
  - Platelets  $\geq 100,000$  cells/mm^3
  - Hemoglobin  $\geq 8.0$  g/dl (Note: The use of transfusion or other intervention to achieve Hgb  $\geq 8$  g/dl is acceptable.)
- n) Pregnancy test must be negative for women of childbearing potential within 7 days prior to study entry
- o) Patient must sign study specific informed consent prior to study entry

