### 3.3 Exclusion Criteria

- a) Prior surgical resection of any pancreatic malignancy
- b) Prior invasive malignancy (except non-melanomatous skin cancer) unless disease free for a minimum of 3 years
- c) Any prior chemotherapy or radiation for treatment of the patient's pancreatic tumor.
- d) Prior radiotherapy to the region of the study cancer that would result in overlap of radiation therapy fields
- e) Severe, active comorbidity, defined as follows:
  1. Unstable angina and/or congestive heart failure requiring hospitalization within the last 12 months
  2. Transmural myocardial infarction within the last 6 months
  3. Acute bacterial or fungal infection requiring intravenous antibiotics at the time of registration
  4. Chronic obstructive pulmonary disease exacerbation or other respiratory illness requiring hospitalization or precluding study therapy within 30 days prior to registration.
- f) Severe, uncorrectable hepatic insufficiency and/or coagulation defects due to liver failure
- g) Any evidence of distant metastases (M1)
- h) Pregnancy or women of childbearing potential and men who are sexually active and not

willing/able to use medically acceptable forms of contraception; this exclusion is necessary because the treatment involved in this study may be significantly teratogenic

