#### **4. METHODS AND STUDY PROCEDURES**

##### **4.1 Pretreatment Evaluation (please see schedule in Appendix B for table layout)**

Within 6 weeks prior to study enrollment patients must undergo the following evaluations:

- a) History and physical by Radiation Oncologist, Gastroenterologist and Surgical Oncologist
- b) CT or MRI scan of the abdomen and pelvis with IV contrast or PET/CT
- c) CT chest or PET/CT within 6 weeks prior to registration
- d) Informed Consent obtained by a member of the study team
- e) Lab studies [CBC with diff, Na, K, BUN, Cr, Glucose, Phosphorous, Calcium, Albumin, AST, ALT, Total bilirubin, Alkaline phosphatase, CA19-9, CEA, INR and a pregnancy test (urine or serum HCG) for women of childbearing potential].
- f) If clinically indicated, fiducial placement in/near the tumor via endoscopic ultrasound by gastroenterology service at least one week prior to CT simulation
- g) Patients will be placed on proton pump inhibitors 1 week prior to SBRT to continue until the day of surgery to minimize bowel toxicity.
- h) Any bile stent manipulation should be done 7-10 days prior to SBRT

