Investigators will conduct continuous review of data and patient safety. The Investigator will submit quarterly progress reports of these data to the Clinical Trials Monitoring Committee for review [Appendix C]. The review will include for each treatment arm/dose level: the number of patients enrolled, withdrawals, significant toxicities as described in the protocol, serious adverse events both expected and unexpected, dose adjustments, and responses observed. The PI maintains a database of all adverse events with toxicity grade and information regarding treatment required, complications, or sequelae. The Investigator will submit a copy of the AE spreadsheet along with the Progress Report to the Clinical Trials Monitoring Committee for review. Actual review dates will be assigned when the 1st patient is accrued.

- Any serious adverse event that is serious, related AND unexpected must be reported within 10 calendar days to both the Safety Coordinator and the RSRB (see RSRB guidelines). The DSMC Chair will determine whether further action is required, and when patient safety is of concern, an interim meeting may be called.
- Serious adverse events that are related AND expected or unrelated AND unexpected will be reported to the Committee for review at the quarterly meeting. SAE reports are expected to include sufficient detail so that the DSMC can determine the severity, toxicity grade, expectedness, treatment required, and a follow up report documenting resolution or if there are sequelae. Unless otherwise specified in the protocol, serious adverse events that require detailed reports (but not necessarily expedited) are expected, related, non-hematologic toxicities of grades 3, 4 or 5.

We plan to publish a descriptive analysis of the results including acute and late toxicity including surgical morbidity. We plan to report oncologic outcomes including median overall survival, progression free survival, local progression free survival and distant progression free survival. Analysis will be using Kaplan-Meier method. Survival time will be measured from the date of diagnosis. A local recurrence will be defined as any evidence of tumor recurrence within the PTV. Whether local recurrence occurred in conjunction with, before or after distant recurrence will be noted.

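### Survival is timed from diagnosis by Kaplan-Meier without delayed entry, so an interval that is event-free by selection counts as time at risk; the bias is probably small and is easily removed

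*Combined protocol and SAP*

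**What the plan says.** Section 9 (Data Analysis and Monitoring) plans to report overall survival (OS), progression-free survival (PFS), local PFS and distant PFS by Kaplan-Meier. The only statement on the clock is "Survival time will be measured from the date of diagnosis". It is not tied to a particular endpoint; the natural reading is that it covers all four. The documents mention no delayed entry, landmark or second time origin.

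Section 3.2 (Inclusion Criteria) requires a "Patient with pathologically proven diagnosis of adenocarcinoma of the head of the pancreas", resectable disease and no distant metastasis. Section 3.3 excludes M1 disease again. The 6-week windows for imaging and work-up in Sections 3.2 and 4.1 run back from registration or enrolment, not forward from diagnosis.

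Section 4.1 contains two lead times. The first is "Patients will be placed on proton pump inhibitors 1 week prior to SBRT". The second is for fiducials, which are placed only where clinically indicated: "at least one week prior to CT simulation".

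Among the secondary objectives in Section 2.3 are "To determine overall survival of treated patients" and "To determine local control and recurrence patterns of treated patients relative to historical controls". The second is the only outcome set against an outside group.

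**The concern.** Kaplan-Meier from diagnosis assumes that a patient could have had an event, and been seen to have it, from the day of diagnosis. Here that is not so. Someone who dies, is found to have metastases or becomes unresectable between diagnosis and registration never enters the study. Everyone who does enter brings an interval with no events, and the planned analysis places that interval in the risk set from time zero. The early part of each curve is flat by construction.

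Local recurrence shows this most plainly. Section 9 defines it as recurrence inside the planning target volume, and that volume does not exist until simulation and planning (Section 4.3.1a). No local recurrence so defined can fall between diagnosis and planning.

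At stake is how the published survival figures are read, and whether local control can fairly be compared with historical controls. The safety and feasibility conclusions do not depend on the clock.

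**Working it through.** **No figure of the plan's own to reproduce.** The documents state no survival estimate, event count or power that depends on the time origin. What follows is an illustration.

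**Inputs**
- One-year OS of 75%, from the proton study described in Section 1. Its time origin is not given; I assume it is timed from SBRT.
- Constant hazard (assumed): λ = −ln(0.75)/12 = 0.02397 per month.
- Gap m from diagnosis to the start of SBRT (assumed): 1 week (0.23 month), 1 month, and 3 months as an outer value. Patients in a treated-patient analysis are necessarily alive throughout this gap.
- Pre-entry hazard as a fraction r of the later hazard (assumed): 1, 0.5, 0.25 or 0.

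**Formulas**
- One-year OS as the planned analysis reads it: exp(−λ(12 − m)).
- True one-year OS from diagnosis: exp(−λ(12 − m + r·m)).
- Bias = the first minus the second.

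**Example, m = 1 month.** The planned analysis reads exp(−0.02397 × 11) = 76.82%. With r = 1 the true value is exp(−0.02397 × 12) = 75.00%, so the bias is 1.82 points. With r = 0.25 the true value is exp(−0.02397 × 11.25) = 76.36%, so the bias is 0.46 points.

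| Gap | Planned analysis reads | Bias, r = 1 | r = 0.5 | r = 0.25 | r = 0 |
|---|---|---|---|---|---|
| 1 week | 75.41% | 0.41 | 0.21 | 0.10 | 0 |
| 1 month | 76.82% | 1.82 | 0.92 | 0.46 | 0 |
| 3 months | 80.59% | 5.59 | 2.85 | 1.44 | 0 |

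**Two quantities to keep apart.** The difference between the second column and 75% is a change of origin: each patient's time is longer by the gap. Only the columns to its right are bias against true survival from diagnosis. The two coincide only when r = 1.

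**Local control.** Section 1 reports local progression in 1 of 15 patients. Treating 14/15 = 93.3% as a crude one-year figure, λ = −ln(14/15)/12 = 0.00575 per month. The change of origin is 0.5 points at 1 month (93.87%) and 1.6 points at 3 months (94.96%). The bias at r = 0.25 is 0.1 and 0.4 points.

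**Scale.** With 12 patients, 9/12 (75%) has an exact 95% interval of 43% to 95%, and a standard error of √(0.75 × 0.25/12) = 12.5 points.

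**Does delayed entry alone repair it?** Only in part. The check was 10,000 simulated trials of 12 patients, with gaps uniform on 0.5 to 1.5 months, r = 1 and no censoring before 12 months. Against a true 75%, the mean one-year estimate was about 76.8% from diagnosis as planned, 76.1% from diagnosis with delayed entry, and 75.0% from SBRT. Delayed entry cannot see the time before the earliest entry.

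**The case against.** The strongest reply is that diagnosis is a legitimate origin for a descriptive survival figure declared in advance, and that the distortion is trivial here. Much of this stands. Section 3.1 recruits patients referred to the centre for diagnosis and work-up, so diagnosis may often fall within the recruitment pathway. Section 3.3 excludes prior chemotherapy or radiation for the tumour. A long untreated gap in resectable disease is therefore speculative. An early death hazard equal to the later one is an extreme case for patients fit for surgery. The lead times in Section 4.1 are counted back from SBRT and CT simulation. They make a week or so plausible, but they do not say how long after diagnosis treatment starts.

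It is also fair that controls who never had SBRT have no first-fraction date. Moving the clock does not by itself make the local-control comparison sound.

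What does not stand is that nothing need change. The error never runs against the treatment, more patients would not remove it, and the secondary objectives concern treated patients, whose treatment begins at the first fraction.

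A reader might go further and infer that the survival results cover only resected patients, so that guaranteed time runs on to surgery. The Schema ("Phase I: 12 patients who undergo SBRT and surgical resection"), the withdrawal rule in Section 4.3.3 and the timing of the efficacy evaluation in Section 9 allow that reading. They do not establish it. Section 2.3 speaks of treated patients, and the sentence in Section 9 says when efficacy is evaluated, not in whom. What the documents support is that the survival analysis set is not stated.

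**Conclusion.** The point holds in modest form. As written, Section 9 counts as time at risk an interval in which no enrolled patient could have had an event. The effect is favourable or nil.

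Its size cannot be derived from the documents. Under the assumptions above, with a pre-entry hazard no higher than the later one, the bias in one-year OS is at most about 0.4 points for a 1-week gap. For a 1-month gap it is 0.5 to 1.8 points when r lies between 0.25 and 1. It vanishes if the pre-entry hazard is zero. All of this is small next to the sampling error of 12 patients, and it is confined to secondary, descriptive endpoints.

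A reader might infer that survival will be materially overstated, by 5 points or more. That needs a 3-month gap and an equal pre-entry hazard, and the documents support neither. Nor should the whole shift from an SBRT clock to a diagnosis clock be read as bias.

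**What to change.** In Section 9:
1. Time OS, PFS, local PFS and distant PFS from the first SBRT fraction, naming the origin for each endpoint.
2. Include every patient who starts SBRT, resected or not, and keep collecting survival status for those withdrawn under Section 4.3.3. The alternative is to time from registration in all enrolled patients, which also keeps those lost before SBRT.
3. Report the diagnosis-to-SBRT interval. If a from-diagnosis curve is kept, use delayed entry and label it supplementary.
4. For the local-control comparison in Section 2.3, choose historical controls with the same time origin and population, or add a supplementary analysis from an origin that those controls share.

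The cost is a few sentences, using dates that the trial will have in any case. Reported survival times become slightly shorter, and survival status must be obtained for unresected patients after they leave the protocol. No patients or study visits are added.

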Building upon this experience, a prospective study of 15 patients from Harvard demonstrated that neoadjuvant short course RT using 25 Gy in 5 fractions to the pancreatic bed and regional lymph nodes using proton therapy and concurrent capecitabine was feasible and well tolerated. Acute grade 3 toxicity was noted in 4 of 15 patients. 11 of 15 patients underwent surgical resection but no patients experienced delays or exclusion from surgery due to toxicity from neoadjuvant treatment. Evaluation of 30 day post-operative results showed no deaths or anastomotic leaks. 9 of 11 patients who underwent surgery had R0 resections and 10 of these patients were able to receive post-operative gemcitabine. After a median follow up of 12 months, one year overall survival was 75% for the entire group. Of 11 surgical resected patients, 10 are still alive at last follow up. Of 15 patients treated with neoadjuvant therapy, only 1 patient with a positive surgical margin experienced local progression. No patient experienced nodal or regional failure but 8 patients developed metastatic disease.

A similar study was repeated, also at Harvard, using photon (conventional x-rays) instead of proton radiation therapy. However, compared with the proton study a higher rate of fibrosis (63% vs. 27%) was noted during surgery leading to a mean increase in operative time of 69

minutes. Dosimetric comparisons revealed that patients undergoing photon irradiation had significantly increased low dose radiation exposure to the abdominal organs. Due to this complication, the study was terminated after accrual of 10 of 12 planned patients.

While the Harvard study with neoadjuvant proton therapy achieved excellent results, protons are not widely available at most centers including ours. Therefore, we believe that there is a need for continued investigation of neoadjuvant photon radiation therapy for pancreatic cancer. We hypothesize that delivering high dose photon radiation to the gross disease using stereotactic localization (SBRT) without elective nodal irradiation can effectively reduce local recurrence while minimizing the fibrosis noted in the Harvard Photon study.

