##### **4.3 Treatment**

###### **4.3.1 Radiation Therapy**

###### **4.3.1a Simulation and Planning**

Patients should abstain from oral intake for 2 hours prior to CT Simulation. Water and medications are acceptable. Patients will be simulated supine and Exac-trac body markers will be placed on the skin for patient positioning and respiratory management. In order to minimize treatment volume, patients will be asked to perform end-expiratory breath hold during simulation and treatment. If patient is unable to tolerate and/or comply with breath hold, simulation and treatment will be done using shallow free breathing. A Vac-bag custom immobilization device will be made.

With the patient in the treatment position and in end-expiratory breath hold, a non-contrast CT will be first performed. This will be followed by a contrast CT scan (if no contraindications) also using breath hold technique. The maximum slice thickness will be 2.5mm. If intravenous contrast is not used during CT Simulation, a diagnostic CT or MRI using intravenous contrast or PET/CT must be available as a reference for target delineation.

Gross tumor volume (GTV) will be defined on the basis of CT and MRI imaging findings. The GTV alone will be treated with a planning target volume (PTV) margin of -5 mm to account for setup inaccuracy and patient and organ movement. If needed, PTV can be reduced to 3mm or less in order to avoid high doses to the duodenum and stomach. 25 Gy in 5 fractions will be prescribed to the 70-90% isodose line. Patients will be treated in 5 fractions delivered over 5-7 days.

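### Local control counts only recurrence inside the PTV, and no rule classifies a bed, margin, anastomotic or regional-nodal recurrence outside it

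*Combined protocol and SAP*

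**What the plan says.** The endpoint definition is one sentence in section 9 (Data Analysis and Monitoring): "A local recurrence will be defined as any evidence of tumor recurrence within the PTV". The sentence after it adds only a rule on timing: "Whether local recurrence occurred in conjunction with, before or after distant recurrence will be noted". Besides overall survival and overall PFS, the outcomes to be reported by Kaplan-Meier are "local progression free survival and distant progression free survival". The protocol does not define distant recurrence, regional recurrence or a progression event.

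Section 4.3.1a fixes how large the PTV is: "The GTV alone will be treated with a planning target volume (PTV) margin", followed by "If needed, PTV can be reduced to 3mm or less in order to avoid high doses to the duodenum and stomach". The hypothesis in section 1 confirms that nodes are not targeted; it is that SBRT "without elective nodal irradiation can effectively reduce local recurrence". Surgery under section 4.3.3 is a Whipple procedure with lymphadenectomy, so the operated region extends beyond the gross tumour.

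Secondary objective (a) in section 2.3 is "To determine local control and recurrence patterns of treated patients relative to historical controls". No section names the historical series, its rate or its definition of local failure. Section 1 describes several earlier studies and designates none as the comparator. For the proton study it reports nodal or regional failure as a class of its own: "No patient experienced nodal or regional failure but 8 patients developed metastatic disease".

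**The concern.** The plan divides recurrence into in-PTV and distant, and leaves the space between them without a rule. A recurrence in the pancreatic bed, at a resection margin, at an anastomosis or in a regional node can lie outside a tight volume drawn around the gross tumour. As written, it is not a local recurrence. Whether it is a distant one would be left to whoever does the analysis, after the data are seen.

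Two results depend on that choice. The first is the local-control figure, which is to be set against historical controls that may have counted such failures. The second is the recurrence pattern, which is the other half of secondary objective (a). The gap touches the trial's own reasoning: if omitting elective nodal treatment has a cost, it would appear as nodal failure, and the local endpoint cannot register it.

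**Working it through.** There is no figure in the plan to reproduce. It states no target, historical rate, alpha or power for local control. The check is a reading of the definitions, followed by arithmetic for scale.

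**1. Where each recurrence goes under the plan as written**

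| Site of recurrence | Counts against local control? | Class assigned |
|---|---|---|
| Inside the PTV | Yes | Local |
| Bed, margin or anastomosis, outside the PTV | No | None stated |
| Regional node, outside the PTV | No | None stated |
| Remote organ | No | Presumably distant (undefined) |

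**2. Direction.** Let L be the number of patients with an in-PTV recurrence and R the number with any locoregional recurrence (in-PTV, or in the bed, margin, anastomosis or regional nodes outside it). Every patient in L is also in R, so L ≤ R and 1 − L/n ≥ 1 − R/n. Crude in-PTV control therefore cannot be lower than crude locoregional control in the same patients. The two are equal if no patient has a locoregional recurrence solely outside the PTV. This ordering is guaranteed for crude proportions; for Kaplan-Meier estimates with censoring it is usual but not guaranteed.

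**3. Scale.** Section 9 plans n = 12 evaluable patients. One reclassified patient is 1/12 = 8.3 points. The documents give no count of out-of-PTV recurrences, so I assume 0 to 3, with no in-PTV recurrence. In-PTV control is then 12/12 = 100% in every row (exact 95% interval 73.5 to 100).

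| Patients with only an out-of-PTV locoregional recurrence (assumed) | Crude locoregional control (exact 95% interval) | Gap, points |
|---|---|---|
| 0 | 12/12 = 100% (73.5 to 100) | 0 |
| 1 | 11/12 = 91.7% (61.5 to 99.8) | 8.3 |
| 2 | 10/12 = 83.3% (51.6 to 97.9) | 16.7 |
| 3 | 9/12 = 75.0% (42.8 to 94.5) | 25.0 |

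The intervals overlap widely. The issue is what the number counts, not a difference that 12 patients could detect.

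**4. How likely the gap in the rules is to matter at all.** If each patient has an independent risk p of an out-of-PTV locoregional recurrence, the chance of at least one among 12 is 1 − (1 − p)^12. For assumed p of 5%, 10%, 20% and 30% this is 46%, 72%, 93% and 99%.

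**5. Local PFS.** If deaths count as events (the plan does not say), a patient with an out-of-PTV recurrence who later dies is an event under either definition, and only the event date differs. The effect is then smaller than on crude local control.

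**The case against.** The best defence is that in-PTV failure is a deliberate and legitimate measure. The study treats gross disease alone, and recurrence inside the treated volume shows directly whether the treatment worked where it was given. That stands: the definition is not an error, and a reader who infers that it should be replaced goes too far.

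A reader might also infer that recurrences outside the PTV drop out of the results altogether. The documents do not support this. Overall PFS would presumably count them, although PFS events are undefined. The list of oncologic outcomes in section 9 is not worded as exhaustive, and objective (a) promises recurrence patterns, which leaves room to describe them. What remains is narrower: they leave local control untouched and have no assigned class.

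Nor does the recording of lymph node and margin status in section 5.2.1 show that a regional failure category was intended. That is pathologic staging at resection, not recurrence data.

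On the comparison, section 9 plans a descriptive analysis with no test, threshold or decision tied to a historical rate, and a later report could state its comparator. This lowers the weight of the point. It does not remove it, because objective (a) commits to the comparison now, and the choice of series and definition would otherwise follow the data.

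Finally, the only regional-failure figure in the documents is none among 15 patients, in the proton study. That study irradiated the bed and regional nodes, so the figure does not carry over to a design that leaves nodes untreated.

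**Conclusion.** The concern holds in limited form. Recurrence in the bed, at a margin, at an anastomosis or in regional nodes, when outside the PTV, does not count against local control, and no rule says how it is classified. Crude local control would therefore look too favourable against any series that counts such failures. It would be more nearly comparable with a series using a similar in-field definition. Because no series is named, a reader of objective (a) cannot tell which case applies.

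The size is unknown and may be zero. The figure of 8.3 points per patient applies to crude control in 12 evaluable patients, and the counts and risks used for scale are assumptions. It would be wrong to infer a bias of known size, or any effect on the trial's main conclusions: feasibility, acute toxicity and surgical morbidity do not use this definition. Severity is minor.

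**What to change.** - Keep in-PTV recurrence as an outcome and label it in-field control.
- Define three mutually exclusive sites: local (pancreatic bed, margin or anastomosis, inside or outside the PTV), regional (regional nodes) and distant (all other sites).
- Report locoregional control beside the in-field figure. With about 12 patients, list every recurrence by site and date.
- For secondary objective (a), name the historical series and use whichever measure matches its definition of failure, or delete the reference to historical controls.

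The cost is small: three definitions, a short listing, one named series or one deleted phrase, and slight extra analysis work. Appendix B already schedules abdominal and pelvic imaging (or PET/CT) at follow-up, and the existing definition already requires each recurrence to be located relative to the PTV. The one real downside for the investigators is that the locoregional figure may be less favourable than the in-PTV figure alone.

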## **3. CHARACTERISTIC OF THE RESEARCH POPULATION**

### **3.1 Subject Characteristics**

We aim to enroll 18 patients into this Phase I trial with the goal of 12 evaluable cases. We will recruit from the population of patients who are referred to URMC for diagnosis and workup of their suspected pancreatic adenocarcinoma. We expect that patients will be approximately 50-70 years old with an equal distribution of males and females and racial and ethnic backgrounds. No vulnerable subjects will be enrolled.

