#### 4.3.3 Surgery

Surgery will be performed no more than 3 weeks after completion of radiation therapy. A pancreaticoduodenectomy (Whipple procedure) with standard lymphadenectomy will be done. Restaging is not required prior to surgery. However if re-staging scans are obtained and demonstrate metastatic disease, surgery will not be performed.

An attempted resection may also be aborted when more advanced or metastatic disease is found at the time of laparotomy. If surgical resection cannot be completed due to the presence of advanced disease, the patient will be withdrawn from the protocol at that time and will continue their care with standard treatment and follow up based on their clinical characteristic.

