## **9. DATA ANALYSIS AND MONITORING**

The purpose of this pilot study is to determine feasibility of preoperative SBRT followed by surgical resection at URMC and to determine its safety and tolerability in a small population of patients. For this phase 1 trial, we plan to enroll 18 patients over 1-2 years with a goal of 12 evaluable cases. This is a generally accepted number of patients for phase 1 trials and will minimize the risks to patients in case the treatment is found to be unsafe. We will stop recruitment and analyze the safety data if there appears to be any grade 3 or greater toxicity on any subject that can be directly attributed to SBRT or if any patients are made ineligible for surgical resection solely due to toxicities from SBRT.

In the case where any patient becomes ineligible for resection due solely to toxicity from SBRT, the study will be immediately closed to accrual. We will stop recruitment and any patient who has not started radiation therapy will have their planned radiation treatment canceled. A patient who has started radiation therapy will undergo an individual discussion with [name] about the risks and benefits of continued treatment.

If a patient experiences grade 3 or greater toxicity directly attributable to SBRT that is reversible and ultimately able to undergo resection, we will analyze the event and attempt to prevent/reduce the adverse event from taking place again. We will discuss the risks and benefits of continued recruitment into the study with our co-investigators and determine whether or not to continue the study. If we believe that modifications can be made that will reasonably reduce the risk of a future event from occurring, we will continue recruitment to the study.

The investigators plan to evaluate the rates of acute toxicity after 12 patients have been enrolled and undergone SBRT and surgical resection. Long term safety and efficacy will be evaluated after all 12 patients have undergone surgical resection and have either been followed for at least 6 month or have died. The primary investigator, [name] will have access to all of the study data.

The Cancer Center Data & Safety Monitoring Committee will monitor the study for safety. Study

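### Patients who progress before or at surgery drop out of PFS, distant PFS and local control, so a resected-only result would be reported under an objective about treated patients

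*Combined protocol and SAP*

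**What the plan says.** Section 9 plans a descriptive report of overall survival, progression-free survival (PFS), "local progression free survival and distant progression free survival". On method it says "Analysis will be using Kaplan-Meier method". The only local event defined is this: "A local recurrence will be defined as any evidence of tumor recurrence within the PTV". Progression is not defined, and no censoring rule or analysis set is given for these outcomes.

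The matching objective, Section 2.3(a), reads "To determine local control and recurrence patterns of treated patients relative to historical controls".

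Section 4.3.3 foresees treated patients who are not resected. On restaging it says "However if re-staging scans are obtained and demonstrate metastatic disease, surgery will not be performed". It also allows a resection to be abandoned at laparotomy. Patients whose resection cannot be completed because of advanced disease then leave the protocol for standard care. Whether their outcome data stay in the analysis is not said.

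The numbers are built on resected patients. The Schema has "Phase I: 12 patients who undergo SBRT and surgical resection", Section 9 has "Long term safety and efficacy will be evaluated after all 12 patients have undergone surgical resection", and Section 3.1 has "We aim to enroll 18 patients into this Phase I trial with the goal of 12 evaluable cases".

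Section 1 describes the proton predecessor: 15 patients treated, 11 resected, and one local progression reported over all 15.

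**The concern.** The objective names one population and the rest of the plan leads to another. A patient who receives SBRT and is then found to have metastases on restaging or at laparotomy is a treated patient with an early progression. Under Sections 4.3.3 and 9 that patient is outside the 12 on whom efficacy is evaluated, and no text makes the finding a dated event. The earliest progressions are therefore the ones that go missing from PFS and distant PFS.

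For local control there is a second gap. Even if such a patient were kept, recurrence is the wrong word for a tumour still in place, and nothing says what counts as its local progression. The result is a resected-only figure under a treated-patients label. The proton predecessor described in Section 1 counts local progression over everyone treated, so a comparison with it would not be like for like.

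**Working it through.** **The plan's own figure.** 18 enrolled for 12 evaluable leaves 18 − 12 = 6, or 6/18 = 33.3%. No attrition rate is stated, so 18 cannot be derived independently: 12/(1 − 6/18) = 18 is circular. The predecessor's unresected rate gives 12/(1 − 4/15) = 16.4, rounded up to 17, which is close to 18. The six are enrolled patients not evaluable for any reason, so six is an upper planning bound on unresected treated patients and not a share of those treated.

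**Unresected share.** The only resection figure is 11 of 15 (Section 1, proton study). Unresected: 4/15 = 26.7%, exact (Clopper-Pearson) 95% CI 7.8% to 55.1%. At that ratio, 12 resected patients go with 12 × 4/11 = 4.4 unresected; I use 4, with a range of 0 to 6.

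**PFS and distant PFS.** Let u be the number of treated patients not resected because metastases were found. Assume no resected patient has progressed by surgery. The proportion progression-free just after the planned surgery is 12/(12 + u) in all treated patients:
- u = 0: 12/12 = 100%
- u = 4: 12/16 = 75.0%
- u = 6: 12/18 = 66.7%

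A resected-only curve shows 100% at this point in every case.

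**Local control.** The documents give no local failure rate for this trial. Assume x = 2 local failures among 12 resected patients, u unresected, and a fraction f of the unresected failing locally. As simple proportions:
- resected only: 1 − x/12 = 1 − 2/12 = 83.3%
- all treated: 1 − (x + f·u)/(12 + u)

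| u | f = 0 | f = 0.5 | f = 1 |
|---|---|---|---|
| 0 | 83.3% | 83.3% | 83.3% |
| 4 | 1 − 2/16 = 87.5% | 1 − 4/16 = 75.0% | 1 − 6/16 = 62.5% |
| 6 | 1 − 2/18 = 88.9% | 1 − 5/18 = 72.2% | 1 − 8/18 = 55.6% |

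The two figures agree when f = x/12 = 2/12 = 16.7%. The resected-only figure is too favourable only if unresected patients fail locally more often than that.

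**Predecessor.** Its one local progression was in a patient with a positive surgical margin, hence a resected patient. Local failure is 1/15 = 6.7% over all treated and 1/11 = 9.1% over resected. On those counts the resected-only figure is the less favourable one, so the direction for local control is not settled by the documents.

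**The case against.** The strongest reply is that the plan is coherent for resected patients: recurrence within the PTV suits them, and they are the ones evaluated. The named endpoint is local progression-free survival, so an analyst could score growth of an unresected tumour as an event. The outcomes are secondary and descriptive, in about 12 patients, with no test or decision rule. All of this is fair, and it limits the weight of the point. It does not remove the mismatch with Section 2.3(a), and it does not restore the early metastatic events to PFS.

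Three stronger readings are tempting and should not be drawn:
- A reader might infer that unresected patients count as locally controlled indefinitely. That needs them to stay in the denominator without an event, whereas the Schema, Section 4.3.3 and Section 9 point to their exclusion.
- A reader might infer the opposite, that they all fail at once because tumour lies in the PTV. The definition requires recurrence, and tumour present from the start is not a recurrence.
- A reader might infer that a third of treated patients are affected. The 6 of 18 is an allowance among enrolled patients, with no reasons given, and could include some never irradiated.

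The toxicity route to non-resection is also largely closed: Section 9 stops accrual if one patient loses eligibility for surgery solely through SBRT toxicity.

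**Conclusion.** The point stands as a mismatch between objective, event definition and evaluated group. Dropping patients whose metastases are found before or at surgery makes PFS and distant PFS too favourable: under the stated assumptions, 100% instead of 75.0% progression-free just after surgery with four such patients. For local control, the label is wrong whichever way the numbers fall. The figure is too favourable only if unresected patients fail locally more often than resected ones. In the illustration, 83.3% resected-only stands against 62.5% to 87.5% in all treated patients.

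These values are bounds under assumed counts, not forecasts. They are crude proportions and not Kaplan-Meier estimates, and the effect is nil if every treated patient is resected. The 26.7% unresected share comes from a different regimen (protons with capecitabine and nodal fields) and has a wide interval. No sample size or error rate is affected.

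**What to change.** In Section 9:
1. Analyse PFS, distant PFS and local control in all patients who received SBRT, report resected patients separately, and use the like-for-like group in any historical comparison.
2. Count metastatic disease found at restaging or laparotomy as a PFS and distant-PFS event on that date, and not as a withdrawal, exclusion or censoring.
3. Keep the PTV-based recurrence definition for resected patients. For unresected patients who received SBRT, define the local event as progression of the irradiated tumour on clinical imaging against the pre-SBRT scan.
4. State that leaving the protocol under Section 4.3.3 ends protocol procedures but not the collection of outcome data from standard-care follow-up.

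The cost is a few sentences, an extra row in the results table, and retrieval of routine scans for a handful of patients. Section 5.1 plans no routine evaluation after SBRT and the surveillance in Section 5.2.2 is placed after surgery, so scan timing for unresected patients will vary and their local event dates will be less precise. Reported PFS and local control may be less favourable.
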